**Table 2 Schedule of activities for Part B**

	Day 1	Day 8	Day 29	Day 91	Day 181 (EoS)	Unscheduled Visit b	ET Visit	Notes
Window (days)	0 a	±1	±3	±14	±14			
Visit	1	Phone Call 1	2	Phone Call 2	Phone Call 3			
Informed consent	X							See Section 10.1.3 for details
Distribution of participant card	X							See Section 8.4.8 for details
Inclusion/exclusion assessment	X							See Sections 5.1 and 5.2 for inclusion and exclusion criteria
Demographics	X							See Section 8.1.1 for more information
Medical history (including vaccination history)	X					X c		See Section 8.1.2 for more information
Concomitant medication/vaccination	X	X	X	X	X	X	X	See Section 6.9 for more information
Vital sign measurements d	X					X		See Section 8.3.2 for more information
Physical examination e	X		X			X	X	See Section 8.3.1 for more information
Pregnancy test f	X							See Section 8.3.3 for more information
Blood sample for immunogenicity (neutralizing titers) and, if needed, for eligibility assessment (~20 mL) g	X		X					See Section 8.2 for more information
SARS-CoV-2 anti-nucleocapsid antibody serology	X h		X					See Section 8.2 for more information
SARS-CoV-2 RT-PCR (swab)	X i					X		See Section 8.4.4.2 for more information
Randomization	X							See Section 6.3 for more information
Study intervention administration (including 30-minute post-vaccination observation)	X							See Section 6.1 for more information
Initiate eDiary for solicited AEs	X							See Section 10.3.6 for more information
Site staff review of eDiary		X						See Section 10.3.6 for more information
Return of the eDiary device			X					See Section 10.3.6 for more information
Recording of AESIs, MAAEs, and SAEs	X	X	X	X	X	X	X	See Section 10.3.6 for more information
Recording of SAEs related to study participation, or to a concurrent GSK medication/vaccine j	X	X	X	X	X	X	X	See Section 10.3.6 for more information
Recording of unsolicited AEs	X	X	X			X k		See Section 10.3.6 for more information
Participant study completion					X			See Section 4.4 for EoS definition

CONFIDENTIAL

219075 (CV2 SARS-COV2-013 BST)  
Protocol Amendment 1 Final

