*AE: adverse event; AESI: adverse events of special interest; EoS: end-of-study; ET: early termination; MAAE: medically attended adverse event; RT-PCR: reverse transcriptase polymerase chain reaction; SAE: serious adverse event; SARS-CoV-2: severe acute respiratory syndrome coronavirus 2*  
*Of note, safety follow-up may be completed via an unscheduled visit as permitted by country regulations.*

- a. If a protocol-related procedure needs to be conducted to confirm eligibility or if the participant is likely to fulfill the eligibility criteria after a period of delay, the study intervention administration may be postponed up to a maximum of 14 days until the result is obtained and/or eligibility can be confirmed.*
- b. In case of acute COVID-19 assessment, the unscheduled visit may be used to collect a SARS-CoV-2 swab for RT-PCR testing. Participants will be asked to contact the site immediately should they experience any symptoms of COVID-19, myocarditis, or pericarditis, and an unscheduled visit may be performed.*
- c. Evaluation and review of present COVID-19 illness history of the participants, including medical records to define the severity of COVID-19.*
- d. Vital sign measurements (temperature, pulse rate, respiration rate, and blood pressure) should be collected before and after study intervention administration on Day 1.*
- e. A complete physical examination including height and weight will be performed on Day 1 prior to study intervention administration. Only symptom-directed physical examinations will be performed if clinically indicated at subsequent visits.*
- f. A urine pregnancy test will be performed on Day 1 for female participants of childbearing potential. Negative confirmation is required prior to study intervention administration.*
- g. Other analyses, such as serum FSH to confirm postmenopausal status, may be performed if required.*
- h. Randomization and study intervention administration may proceed before the anti-nucleocapsid antibody results are available.*
- i. A SARS-CoV-2 swab for RT-PCR testing should be obtained at Day 1 to establish baseline characteristics. Randomization and study intervention administration may proceed before the results are available.*
- j. SAEs related to study participation, or to a concurrent GSK medication/vaccine, should be collected from the time that informed consent is obtained (prior to study intervention administration) until the participant is discharged from the study.*

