- k. Unsolicited AEs will only be collected if the unscheduled visit occurs within Days 1 through 28 after vaccination.*

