**Table 6      Objectives and endpoints for Part B**

Primary Safety Objective	Primary Safety Endpoints (population summary)
To evaluate the safety and reactogenicity of three CV0801 booster vaccine manufacturing specifications	
Solicited events:
 
 
Occurrence of solicited administration site and systemic AEs within 7 days (i.e., from Day 1 to Day 7 included) of study intervention administration (percentage of participants)
 
 
Unsolicited events:
 
 
Occurrence of unsolicited AEs within 28 days (i.e., from Day 1 to Day 28 included) of study intervention administration (percentage of participants)
 
 
SAEs, AESIs and MAAEs:
 
 
Occurrence of MAAEs, SAEs and AESIs from Day 1 through the end of the study (approximately 180 days after the study intervention administration), each summarized separately (percentage of participants)
 

Primary Immunogenicity Objective	Primary Immunogenicity Endpoint
To evaluate the immunogenicity of three CV0801 booster vaccine manufacturing specifications	
 
Serum neutralization titers against pseudovirus bearing specific CCI spike protein at Day 29 (GMT)
 

AE: adverse event; AESI: adverse events of special interest; GMT: geometric mean titer; MAAE: medically attended adverse event; SAE: serious adverse event

Complementary details on estimands such as impact of intercurrent events is provided in Section 9.

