#### 8.4.1. Time period and frequency for collecting AE, SAE, and other safety information

All solicited AEs will be collected for a 7-day follow-up period after study intervention administration (i.e., from Day 1 through Day 7).

All unsolicited AEs will be collected for a 28-day follow-up period after study intervention administration (i.e., from Day 1 through Day 28).

All SAEs, MAAEs and AESIs will be collected from the start of study intervention until study end.

SAEs assessed as related to study participation (e.g., study intervention, protocol-mandated procedures, invasive tests, or change in existing therapy) or related to a GSK product (non-investigational medicinal product [IMP]) will be recorded from the time a participant consents to participate in the study until study end.

Medical occurrences that begin before the start of study intervention but after obtaining informed consent will be recorded as medical history/current medical conditions, not as AEs.

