### 10.3.4. **Unsolicited AEs**

#### Definition of Unsolicited AE

- An unsolicited AE is an AE that was either not included in the list of solicited events or could be included in the list of solicited events but with an onset outside the specified period of follow-up for solicited events. Unsolicited AEs must have been communicated by participants who have signed the informed consent. Unsolicited AEs include both serious and nonserious AEs.

- Potential unsolicited AEs may be medically attended (i.e., symptoms or illnesses requiring a hospitalization, emergency room visit, or visit to/by a healthcare provider). The participants will be instructed to contact the site as soon as possible to report MAAE(s), as well as any events that, though not medically attended, are of participants' concern. Detailed information about reported unsolicited AEs will be collected by qualified site personnel and documented in the participant's records.
- Unsolicited AEs that are not medically attended or perceived as a concern by the participant will be collected during an interview with the participant and by review of available medical records at the next visit.

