#### **10.3.6.2. Time period for collecting and recording AEs, SAEs, MAAEs, AESIs and pregnancies**

All solicited events that occur during the 7-day follow-up period after study intervention administration (Day 1 to Day 7) must be recorded into the eDiary, irrespective of intensity. An automatic reminder to complete the eDiary will be sent to the participants during this timeframe. All other AEs occurring within this timeframe should be recorded into the appropriate section of the eCRF, irrespective of their intensity or whether or not they are considered related to the study intervention.

All unsolicited AEs that occur during the 28-day follow-up period after study intervention administration (Day 1 to Day 28) must be recorded into the appropriate section of the eCRF, irrespective of their intensity or whether or not they are considered related to the study intervention.

The time period for collecting and recording SAEs, MAAEs and AESIs will begin at the first receipt of study interventions and will end approximately 6 months after the last administration of the study interventions (at study end). The SAEs related to study participation or to a concurrent GSK medication/vaccine will be collected from the time consent is obtained until the participant is discharged from the study.

All AEs/SAEs leading to withdrawal from the study and pregnancies will be collected and recorded from the time of the first receipt of study intervention until the participant is discharged from the study (refer to Section 10.3.6.6 for details on follow-up of pregnancies). SAEs related to study participation or to a concurrent GSK medication/vaccine will be collected from the time informed consent is obtained until the

participant is discharged from the study. However, if the investigator learns of any SAE related to study participation after a participant has been discharged from the study, the investigator must promptly notify the sponsor.

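### The schedules carry no unsolicited-AE recording at early termination or after an early Visit 2, which conflicts with the required Day 1–28 collection and can slightly under-count one primary safety endpoint

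*Protocol*

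**What the plan says.** **The endpoint.** Unsolicited AEs are one of the primary safety endpoints in both parts (protocol Tables 5 and 6): "Occurrence of unsolicited AEs within 28 days (i.e., from Day 1 to Day 28 included". They are analysed on the Exposed Set (protocol Section 9.2) and reported as a percentage of participants with an exact 95% CI (SAP Section 4.2.1.2).

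**The text.** Section 8.4.1: "All unsolicited AEs will be collected for a 28-day follow-up period after study intervention administration". Section 10.3.6.2: "All unsolicited AEs that occur during the 28-day follow-up period after study intervention administration (Day 1 to Day 28) must be recorded". Neither makes an exception for early leavers or for an early Visit 2. Section 10.3.4 asks participants to report medically attended events, and any others that concern them, as soon as possible. For the rest, "Unsolicited AEs that are not medically attended or perceived as a concern by the participant will be collected during an interview with the participant", together with record review, at the next visit.

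**The schedules.** In Tables 1 and 2 the row "Recording of unsolicited AEs" is marked at Day 1, Day 8, Day 29 and the unscheduled visit. It is blank at Day 91, Day 181 and ET. The row "Recording of AESIs, MAAEs, and SAEs" is marked in every column, ET included.

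**The unscheduled visit.** A note under each table says that "safety follow-up may be completed via an unscheduled visit as permitted by country regulations". Footnote k of Table 2 (l in Table 1) then restricts it: "Unsolicited AEs will only be collected if the unscheduled visit occurs within Days 1 through 28 after vaccination".

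**The Visit 2 window.** Tables 3 and 4 allow Visit 2 at 28±3 days after Visit 1.

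**The concern.** The text defines a closed 28-day window, but the schedule gives no contact that closes it for two kinds of participant.

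- **Early leavers.** Someone who attends an ET visit between the Day 8 contact and Day 28 is seen at a contact where AESIs, MAAEs and SAEs are recorded but unsolicited AEs are not.
- **Early Visit 2.** Someone whose Visit 2 falls on Day 26, 27 or 28 has been asked before the window ends, and no later scheduled contact carries the row. Read literally, the footnote also stops an unscheduled visit on Day 30 from recording an event that began on Day 27.

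Protocol Section 8 makes adherence to the schedule a requirement, so a site following the tables would fall short of Sections 8.4.1 and 10.3.6.2. Any error runs in one direction: fewer events are recorded than occurred. The SAP does not say how a participant with an incompletely covered window is counted. In an Exposed Set tabulation, a participant with no recorded event would ordinarily appear as having none.

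**Working it through.** **1. Visit 2 window.** 28±3 days after Day 1 is 25 to 31 days after, i.e. study Days 26 to 32. This agrees with Day 29±3 in the schedules. Three of the seven permitted days (26, 27, 28) do not lie beyond the window.

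**2. Uncovered time after an early Visit 2.**
- Visit on Day 26, 27 or 28: 2, 1 or 0 full days remain, or 3, 2 or 1 if the visit day itself is counted as unobserved.
- Worst case: 3/28 = 10.7% of the window.
- If Visit 2 is spread evenly over the seven days (an assumption), the average uncovered share is 3/(7×28) = 1.5% counting full days only, or 6/(7×28) = 3.1% counting the visit day.

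**3. What the blank ET cell costs an early leaver.** Take Day 8 as the last marked contact. An ET mark could recover min(ET day, 28) − 8 days.
- ET on Day 9: 1 day.
- ET on Day 18: 10 days.
- ET on Day 28: 20 days.

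Time after departure, 28 minus the ET day, is not recoverable by any mark.

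**4. Effect on the reported percentage.** None of the following inputs is in the documents:
- true 28-day risk p of 10% to 40%, with constant hazard;
- Visit 2 day evenly spread, with the visit day counted as unobserved;
- a fraction d of participants leaving, observed only to Day 8;
- every event in uncovered time missed.

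Let R(t) = 1 − (1 − p)^(t/28). For participants who stay, the observed risk is [R(25) + R(26) + R(27) + 4·R(28)]/7. Overall it is (1 − d) times that, plus d·R(8).

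Example with p = 20%: R(25) = 0.1806, R(26) = 0.1871, R(27) = 0.1936, R(28) = 0.2. The mean is 0.1945, a fall of 0.55 points. With d = 5% and R(8) = 0.0618, the observed risk is 0.95×0.1945 + 0.05×0.0618 = 0.1878, a fall of 1.22 points.

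| True 28-day risk | Fall, no leavers | Fall, 2% leave | Fall, 5% leave | 95% half-width, n = 83 |
|---|---|---|---|---|
| 10% | 0.29 | 0.43 | 0.63 | 6.5 |
| 20% | 0.55 | 0.82 | 1.22 | 8.6 |
| 30% | 0.78 | 1.17 | 1.75 | 9.9 |
| 40% | 0.96 | 1.47 | 2.23 | 10.5 |

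Entries are percentage points. The half-width is 1.96·√(p(1−p)/83), a normal approximation used only for scale. In the extreme case of every Visit 2 on Day 26 and 5% leaving, the fall is 1.3 to 4.5 points.

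These figures are at the upper end. They treat every event in uncovered time as missed, and they charge leavers with time after departure that no schedule entry could recover.

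**The case against.** The strongest reply is that what is missing is a tick mark, not necessarily the inquiry.

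- **The text already requires collection.** The row's Notes cell points to Section 10.3.6, where Day 1–28 recording is mandatory. *This stands, but it is the conflict itself: a site cannot satisfy both the table and the text.*
- **Participants are questioned at ET anyway.** MAAE recording and a symptom-directed examination are marked there, and Section 10.3.6.1 has each unsolicited AE queried for medical attention. *This makes a complete omission unlikely. It does not make recording of non-attended events a scheduled item.*
- **Section 10.3.4 routes remaining events to the next visit.** *In Part A that is Visit 3, so the text covers an early Visit 2, though with long recall and against a blank cell. In Part B only phone calls follow Visit 2, so the gap is more real.*
- **Most clinically important events are still captured.** SAEs, MAAEs and AESIs are recorded at every contact, AEs leading to withdrawal until discharge, and events of concern by spontaneous report. *This stands, and it limits the loss to non-serious, non-attended, unreported events that did not prompt withdrawal.*
- **Earlier events already count.** The endpoint is a percentage of participants, so a missed later event changes nothing for anyone with an unsolicited AE already recorded. *This stands.*
- **A Day 91 question has little value.** In Part B that call falls on Days 77–105, some 7 to 11 weeks after the days in question. *This stands, and makes it the weaker part of the remedy.*

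**Conclusion.** The inconsistency between the schedules and Sections 8.4.1 and 10.3.6.2 is plain in the documents and touches a primary safety endpoint, so it is worth correcting. The effect is small: about 0.3 to 1.0 points per arm from early Visit 2 alone, and 0.6 to 2.2 points with 5% leaving before Day 29. Both ranges rest on the assumed risks, dropout and visit spread above, and both are well inside the sampling uncertainty at 83 per arm.

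The documents do not support four stronger readings that a reader might infer:

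- **That primary safety as a whole is under-collected.** Only the unsolicited-AE endpoint is exposed. Solicited AEs, MAAEs, SAEs, AESIs and AEs leading to withdrawal are not affected.
- **That the blank ET cell loses up to 20 of 28 days for someone who leaves just after the Day 8 call.** Nearly all of that time follows departure. The cell matters most when ET falls near Day 28.
- **That 2 or 3 early leavers in 83 would mean a loss of 2.4 to 3.6 points (2/83 to 3/83).** That dropout count is not in the documents, and each leaver would need a first event of exactly the uncaptured kind before leaving.
- **That the comparison between arms is biased.** The schedule is the same for all arms within a part, and the study is observer-blind.

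**What to change.** 1. In Tables 1 and 2, add an X for unsolicited AEs at the ET visit, with a footnote limiting it to onsets from Day 1 through Day 28. This is the main change.
2. Reword footnote l (Table 1) and footnote k (Table 2) so that the limit applies to the date of event onset, Days 1–28, and not to the date of the unscheduled visit.
3. Where Visit 2 took place before Day 29, ask at the next existing contact about onsets from Visit 2 through Day 28.

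A sentence in the SAP on how participants with incomplete 28-day follow-up are counted or reported would be a useful companion, but the correction does not depend on it.

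**Cost.** A few table and footnote edits and a line of CRF guidance. No visit, window or blood draw is added. There is a small recording burden, and recall at Day 91 is limited. Participants lost to follow-up have no ET contact and are not recovered.

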**Table 3 Intervals between study visits for Part A**

Interval	Planned visit interval	Allowed interval range
Visit 1 (Day 1)→Phone call / CCI CCI (Day 8)	7 days	7±1 day
Visit 1 (Day 1)→Visit 2 (Day 29)	28 days	28±3 days
Visit 1 (Day 1)→Visit 3 (Day 91)	90 days	90±7 days
Visit 1 (Day 1)→Visit 4 (Day 181)	180 days	180±7 days

If the study intervention date is different from the ICF signature date, the study intervention date needs to be taken as a reference for calculating intervals relative to subsequent visits.

Interval is computed as the difference between 2 dates.

**Table 4 Intervals between study visits for Part B**

Interval	Planned visit interval	Allowed interval range
Visit 1 (Day 1)→Phone call 1 (Day 8)	7 days	7±1 day
Visit 1 (Day 1)→Visit 2 (Day 29)	28 days	28±3 days
Visit 1 (Day 1)→Phone call 2 (Day 91)	90 days	90±14 days
Visit 1 (Day 1)→Phone call 3 (Day 181)	180 days	180±14 days

If the study intervention date is different from the ICF signature date, the study intervention date needs to be taken as a reference for calculating intervals relative to subsequent visits.

Interval is computed as the difference between 2 dates.

## 2. INTRODUCTION

### 2.1. Background

Coronavirus disease 2019 (COVID-19) caused by severe acute respiratory syndrome coronavirus 2 (SARS-CoV-2) was declared a pandemic by the World Health Organization (WHO) on 11 March 2020 [WHO, 2020]. As of 9 February 2023, more than 755 million cases have been reported worldwide, leading to more than 6.8 million deaths [WHO, 2023], although this is likely to be substantial underestimate of the true burden of disease [WHO, 2021a]. On 30 January 2023, the WHO Director-General concurred that the ongoing COVID-19 pandemic continues to constitute a public health emergency of international concern [WHO, 2023].

By December 2020, the United States (US) Food and Drug Administration (FDA) and European Medicines Agency (EMA) authorized the first vaccines containing Ancestral strain spike proteins. Since then, the emergence of SARS-CoV-2 variants (e.g., Delta and Omicron) that have the potential to escape immunity conferred by the originally approved vaccines prompted the need for continued development of COVID-19 mRNA vaccines to provide protection against circulating variants of concern [Garcia-Beltran, 2021; Zhou, 2021]. Accumulating real world data substantiate both the protective benefits of mRNA COVID-19 vaccines over non-mRNA vaccines [Self, 2021], and the need for additional doses beyond the primary series due to waning immunity. At least 126 countries worldwide have issued recommendations on booster or additional vaccinations [WHO, 2021b].

In partnership with CureVac AG, GlaxoSmithKline Biologicals S.A. (GSK) developed CV0501, a monovalent modified-nucleoside mRNA COVID-19 vaccine encoding the CCI spike protein, which was a circulating variant of concern [CDC, 2023]. The Phase 1 study for CV0501, study 218595 (CV2 SARS-COV2-012 BST), entitled "*A Phase 1, Open-label, Safety and Immunogenicity Study of a Booster Dose of the Investigational CV0501 mRNA COVID-19 Vaccine in Adults at Least 18 Years Old*" is currently ongoing and its interim analyses provided the basis for the design of this Phase 2 study.

In June 2022, the Vaccines and Related Biological Products Advisory Committee (VRBPAC) recommended that COVID-19 vaccine strain composition be updated to include the dominant circulating variant of concern, Omicron BA.4-5 [Marks, 2022]. Subsequently, Moderna and Pfizer-BioNTech obtained authorization for their bivalent formulations to be used as a single booster dose in select populations [FDA, 2022].

Due to the June 2022 VRBPAC recommendation to change from monovalent to bivalent COVID-19 booster vaccination, CureVac and GSK have developed CV0701, a bivalent modified-nucleoside mRNA COVID-19 vaccine encoding the CCI and CCI. It is an admix of 2 monovalent modified-nucleoside mRNA COVID-19 vaccines; CV0601 CCI) and CV0801 CCI CCI. CCI

CCI The vaccines are intended to be administered intramuscularly as a single booster dose for prevention of COVID-19 caused by SARS-CoV-2.

## 2.2. Study rationale

### 2.2.1. Study rationale for Part A

**Within this Phase 2 study**, the purpose of **Part A** is to evaluate the safety, reactogenicity and immunogenicity of CV0701 and CV0601 **in** healthy adults who have previously received a complete primary vaccination series with or without booster dose(s). By including both bivalent and monovalent vaccine candidates, the study will also provide information on possible immune interference between the CCI and CCI spike protein antigens encoded in the bivalent vaccine (CV0701), compared with the CCI spike protein antigen solely encoded in the monovalent vaccine (CV0601). Within the study, CV0701 and CV0601 will be compared to CCI CCI in a randomized observer-blinded fashion.

